#### **4.4.4. Selection of Doses in the Study**

**Table 3: Dosing and Administration**

Group	Product Name	Dose	Route	Volume	Frequency of Administration
Stage 1					
1	GRT-C907	$5 \times 10^{10}$ vp	IM	0.5 mL	D1
	GRT-R908	30 µg	IM	0.5 mL	D29
3A	GRT-R908	30 µg	IM	0.5 mL	D1, D29
3B	GRT-R908	30 µg	IM	0.5 mL	D1
	GRT-R908	3 µg	IM	0.25 mL	D85-130
4	GRT-R910	10 µg	IM	0.5 mL	D1

Group	Product Name	Dose	Route	Volume	Frequency of Administration
	GRT-R910	3 µg	IM	0.25 mL	D85-130
Stage 2					
5	GRT-R910	3 µg	IM	0.25 mL	D1
6	GRT-R910	6 µg	IM	0.25 mL	D1
7A	GRT-R910	10 µg	IM	0.5 mL	D1
7B	GRT-R910	10 µg	IM	0.5 mL	D1
8A	GRT-R910	10 µg	IM	0.5 mL	D1, D57
8B	GRT-R910	10 µg	IM	0.5mL	D1, D57
9	GRT-R910	3 µg	IM	0.25 mL	D1
10A	GRT-R910	6 µg	IM	0.25 mL	D1
10B	GRT-R910	6 µg	IM	0.25 mL	D1
11A	GRT-R910	10 µg	IM	0.5 mL	D1
11B	GRT-R910	10 µg	IM	0.5 mL	D1
12A	GRT-R910	10 µg	IM	0.5 mL	D1, D57
12B	GRT-R910	10 µg	IM	0.5 mL	D1, D57
13	GRT-C909	$5 \times 10^{10}$ vp	IM	0.5 mL	D1
14	GRT-C909	$1 \times 10^{11}$ vp	IM	0.5 mL	D1
15	GRT-C909	$5 \times 10^{11}$ vp	IM	1.0 mL	D1

#### 4.4.5. Selection and Timing of Dose for Each Participant

Groups 1 and 3A will receive vaccinations on Days 1 and 29+/-3 post-enrollment. Groups 3B and 4 will receive vaccinations on Days 1 and 85+45. The remaining groups 5, 6, 9-11, 13-15 will receive a single vaccine on Day 1.

#### 4.4.6. Blinding

Participants and site staff will be unblinded to participants' vaccination arm assignments in Stage 1 and Stage 2.

#### 4.4.7. Prior and Concomitant Therapy

Concomitant medications will include all current medications and medications taken in the 30 days prior to signing the informed consent form (ICF) for the duration of the study. Medications reported in the electronic case report form (eCRF) are limited to those taken within 30 days prior to the first study vaccination and for 12 months after the last study vaccination. Prescription and over-the-counter drugs will be included as well as herbals, vitamins, and supplements. In addition, receipt of any non-study vaccines will be solicited for the entire duration of the study and reported in the eCRF. Use of a new medication should prompt evaluation for the occurrence of any medication associated adverse effects, including a new diagnosis of chronic medical disease or condition.

Medications that might interfere with the evaluation of the investigational product(s) should not be used during the trial-reporting period (until approximately 12 months after the last study vaccination) unless clinically indicated as part of the participant's health care. Medications in this category include the prohibited medications per the Participant Exclusion Criteria (see protocol Section 5.1.3). In addition, the site PI or appropriate sub-investigator may identify other medications that should not be used due to a risk to participant safety or assessment of reactogenicity and immunogenicity.

Concomitant medications will be reviewed at each study visit/contact, from screening to the Study Day 394 for groups 1 and 3A, Study Day 450 for groups 3B and 4, and Study Day 366 for groups 5, 6, 9-11, and 13-15. Interim medical history will also be reviewed at each visit, including an assessment for new medical conditions requiring the use of concomitant medications. Participants will be provided with a Memory Aid and other study-related materials to record daily oral temperature, solicited injection site and systemic reactions, unsolicited AEs, and concomitant medications. Memory Aids will be reviewed with the participants via telephone, email, or text for contact visits. Based on the information collected, participants may be asked to return to the clinic for an evaluation. Administration of any medications, therapies or vaccines will be recorded on the appropriate DCF.

#### **4.4.8. Treatment Compliance**

Participants will be directly observed at the time of dosing by a member of the clinical research team who is licensed to administer the study product. Administration will be documented on the appropriate data collection form and entered on the eCRF.

### **4.5. Immunogenicity and Safety Variables**

#### **Immunogenicity**

##### Humoral Immunogenicity Assays

The following humoral immunogenicity assays may be performed:

- IgG ELISA antibody binding assays to SARS-CoV-2 proteins (may include nucleocapsid protein, and multiple variant receptor binding domains and variant spike proteins).
- Neutralization assays using SARS-CoV-2 variant specific S-pseudotyped viruses.
- Neutralization assays using different strains of live SARS-CoV-2 (focus reduction neutralization test).
- ChAd68-specific neutralization assay in participants who receive the ChAd-S and ChAd-S-TCE vaccines.

Data at the following time points, or a subset, may be analyzed:

- Stage 1, Groups 1 and 3A: Days 1 and 29 post Dose 1 and Days 29, 181, and 366 post Dose 2
- Stage 1, Groups 3B and 4: Days 1, 29, 57, and 85-130 post Dose 1 and Days 15, 29, 85, 181, and 366 post Dose 2
- Stage 2, Groups 5-7A\*, 7B\*, 9, 10A, 10B, and 11A, 11B, and 13-15: Days 1, 15, 29, 85, 181, and 366 post study vaccination

- Stage 2, Groups 8A\*, 8B\* and 12A\*, 12B\*: Days 1, 15, 29, and 57 post Dose 1 and Days 15, 29, 85, 181, and 366 post Dose 2

*\* After protocol version 9.0 was implemented, it was decided not to enroll participants into Groups 7 and 8 because of competing priorities and predicted difficulties enrolling into these two groups. Group 12 was also not enrolled.*

### Cellular Immunology Assays

This trial may investigate T cell immune responses using the IFN- $\gamma$  ELISpot assay and Intracellular Cytokine Staining (ICS). Time points analyzed may include the following or a subset:

#### ICS

- Stage 1, Groups 1 and 3A: Days 1 and 29 post Dose 1 and Day 29 post Dose 2
- Stage 1, Groups 3B and 4: Days 1, 29, and 85-130 post Dose 1 and Day 15 post Dose 2
- Stage 2, Groups 5-7A\*, 7B\*, 9, 10A, 10B, 11A, 11B, and 13-15: Days 1 and 15 post study vaccination
- Stage 2, Groups 8A\*, 8B\*, and 12A\*, 12B\*: Days 1, 15, and 57 post Dose 1 and Day 15 post Dose 2

#### ELISpot

- Stage 1, Groups 1 and 3A: Days 1 and 29 post Dose 1 and Days 29, 181, and 366 post Dose 2
- Stage 1, Groups 3B and 4: Days 1, 29, and 85-130 post Dose 1 and Days 15, 29, 85, 181, and 366 post Dose 2
- Stage 2, Groups 5-7A\*, 7B\*, 9, 10A, 10B, 11A, 11B, and 13-15: Days 1, 15, 29, 85, 181, and 366 post study vaccination
- Stage 2, Groups 8A\*, 8B\*, and 12A\*, 12B\*: Days 1, 15, 29, and 57 post Dose 1 and Days 15, 29, 85, 181, and 366 post Dose 2

The antigen-specificity of memory B cell responses may also be assessed at late timepoints (6 and/or 12 months post-vaccination) using a Spike multimer binding assay and/or IgG ELISpot.

*\* After protocol version 9.0 was implemented, it was decided not to enroll participants into Groups 7 and 8 because of competing priorities and predicted difficulties enrolling into these two groups. Group 12 was also not enrolled.*

### **Safety**

All safety endpoints for this trial are obtained by reporting of adverse events (solicited or unsolicited) and clinical laboratory results.

#### Adverse Events

AE means any untoward medical occurrence associated with the use of an intervention in humans, whether or not considered intervention-related [21 CFR 312.32 (a)]. An AE can therefore be any unfavorable and unintended sign, symptom or disease temporally associated with the use of medicinal (investigational) product.

Any medical condition that is present at the time that the participant is screened will be considered as baseline and not reported as an AE. However, if the severity of any pre-existing medical condition increases, it will be recorded as an AE.

AEs can be further divided into solicited AEs and unsolicited AEs. Solicited AEs are those that are described in the package insert as local or systemic reactogenicity occurring in the first 7 days after vaccination. Unsolicited AEs are those events that the participant reports occurring without being queried about the specific event.

AEs will be assessed for severity and relationship to study intervention. Reporting of all AEs, solicited and unsolicited, will occur during the period from study product administration on Day 1 through 28 days after each vaccination. After 28 days post last vaccination through the end of study, only SAEs, protocol specified AESIs (including PIMMCs, MAAEs, and NOCMCs), and AEs leading to withdrawal from the study will be reported.

All AEs, solicited and unsolicited, will be captured on the appropriate DCF. Solicited AEs will be regarded as related to the study product and will not require separate entry into the AE log. Information to be collected for unsolicited AEs includes event description, date of onset, assessment of severity, relationship to study product and alternate etiology (assessed only by those with the training and authority to make a diagnosis and listed on the Form FDA 1572 as the participating site PI or appropriate sub-investigator), date of resolution, seriousness, and outcome. AEs occurring during the study-collection and reporting period will be documented appropriately regardless of relationship.

AEs will be followed to resolution or stabilization.

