### 9.3.1. Solicited Events and Symptoms

Systemic solicited AEs were collected pre-vaccination, and systemic and local solicited AEs were collected 30 minutes post-vaccination and then daily for 7 days after each vaccination. Solicited local events include erythema (redness), induration (hardness)/edema (swelling), pain, and tenderness. Solicited systemic events include fever, chills (feverishness), fatigue (tiredness), malaise (general unwell feeling), myalgia (body aches/muscular pain exclusive of the injection site), arthralgia (joint pain exclusive for the injection site), headache, nausea, and diarrhea. Solicited events were graded on a scale of none (absent), mild, moderate, and severe. Measurement values for erythema and induration (hardness)/edema (swelling) were collected and graded based on the FDA Toxicity Grading Scale for Healthy Adult and Adolescent Volunteers Enrolled in Preventative Vaccine Clinical Trials [[4](#)].

Solicited AEs are summarized by severity pre-vaccination (systemic solicited AEs only), post-vaccination, and each day post-study vaccination (Days 1-8). Solicited AEs are also summarized by the maximum severity over all post-vaccination measurements. The proportions of participants reporting each symptom, any local symptom, any systemic symptom, and any symptom are summarized by vaccination arm separately for each dose and both doses combined (where applicable). For each event the denominator is the number of participants with non-missing data for the event.

The following summaries for solicited adverse events are presented by maximum severity, vaccination (each dose separately and both doses combined, where applicable), and vaccination arm:

- Number and percentage of participants experiencing solicited events by symptom and maximum severity, for any symptom, local symptoms, and systemic symptoms (beginning with [Table 222](#) and ending with [Table 230](#))
- Number and percentage of participants experiencing any solicited event, any systemic event, any local symptom, and each symptom, by day and severity, for each vaccination (starting with [Table 231](#) and ending with [Table 250](#))

- Duration of solicited symptoms summarized by mean, standard deviation, median, minimum, and maximum by symptom, dose, and vaccination arm ([Table 251](#), [Table 252](#), [Table 253](#), [Table 254](#), and [Table 255](#))

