## 16.2.7 Adverse Events

### Listing 9: 16.2.7.1: Solicited Events – Systemic Symptoms

Vaccination Arm	Participant ID	Dose Number	Post Dose Day	Assessment a	Symptom	Severity	Attributed to Alternate Etiology? b	Alternate Etiology
				MA				
				Clinic				

a MA = Data reported by participant on the Memory Aid and reviewed by clinic staff and reported in Solicited Events eCRF.  
b Grade 3 events only.  
Note: Clinic = Data collected by clinic staff during physical exam or symptom assessment (treatment administration record, in-clinic assessment, etc.)

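### The main solicited-symptom rates use only the worst post-dose grade, so a systemic symptom unchanged from its recorded pre-dose grade counts as a post-vaccination event

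*SAP*

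**What the plan says.** On collection, SAP Section 9.3.1 states: "Systemic solicited AEs were collected pre-vaccination, and systemic and local solicited AEs were collected 30 minutes post-vaccination and then daily for 7 days". The pre-dose grade is thus available for every systemic solicited symptom, but not for the local ones.

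On counting, the same section states: "Solicited AEs are also summarized by the maximum severity over all post-vaccination measurements". The shell for Tables 222-230 follows this. Its footnote defines severity as the post-dosing maximum, and it has no pre-dose column. Tables 212-216 count participants with at least one systemic solicited event and state no baseline condition.

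The pre-dose grades appear in two other places. Tables 231-250 have a Pre-Dose column beside the daily post-dose columns. Listing 9 shows systemic symptoms by participant, dose and day, and its implementation note includes baseline assessments.

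Two rules in Section 4.5 (Adverse Events) lie close to this point. On pre-existing conditions: "Any medical condition that is present at the time that the participant is screened will be considered as baseline and not reported as an AE", followed by "However, if the severity of any pre-existing medical condition increases, it will be recorded as an AE". On causality: "Solicited AEs will be regarded as related to the study product and will not require separate entry into the AE log".

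**The concern.** The trial has no control group (Section 4.2), so there is no concurrent background rate of headache, fatigue or joint pain. The participant's own grade just before the injection is the only within-trial reference at the time of dosing. It is collected, but the summaries a reader will use to compare doses do not draw on it. A participant with mild arthralgia before dosing and the same mild arthralgia afterwards appears in Tables 222-230 as having mild post-vaccination arthralgia, and in Tables 212-216 as having had a systemic solicited event.

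Safety is the primary endpoint (Section 8.1), and the primary objective concerns safety and tolerability at different doses (Table 1). Table 2 gives groups of 3 to 12. At that size one or two carried-over complaints can create or mask an apparent step between neighbouring dose levels.

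**Working it through.** **Where the inclusion arises.** Consider a symptom graded mild before dosing and mild on each day after.

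- Section 9.3.1 and the Table 222 footnote take the maximum over post-dose measurements. The result is mild, and the participant is counted.
- The relatedness sentence in Section 4.5 has no effect on this. Tables 222-255 have no relationship column. In Tables 212-216 relationship is split only for unsolicited and serious events, and the solicited rows carry NA. Deleting the sentence would leave every solicited rate as it is.
- The Pre-Dose column of Tables 231-250 is a group count. It does not show whether those counted before dosing are the same people counted afterwards.
- Listing 9 does link the two, but only by hand, participant by participant.

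**Weight of one participant.** The weight is 100/n points, with n from Table 2: 100/12 = 8.3, 100/10 = 10, 100/7 = 14.3 and 100/3 = 33.3. The last applies only to Groups 3A and 4. This is the shift for a participant who would not otherwise have reacted; one who would have reacted anyway adds nothing to the count. In a group of 10, such a shift takes 2/10 (20%, Clopper-Pearson 2.5 to 55.6%) to 3/10 (30%, 6.7 to 65.2%).

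**Effect on the expected rate.** Let p be the true new-onset rate and b the proportion with a pre-dose symptom that persists unchanged. The SAP gives neither, so both are assumptions, taken as independent. The counted rate is 1 - (1 - p)(1 - b), and the excess is b(1 - p).

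| b (assumed) | counted rate if p = 20% | counted rate if p = 60% |
|---|---|---|
| 2% | 21.6% | 60.8% |
| 5% | 24.0% | 62.0% |
| 10% | 28.0% | 64.0% |
| 20% | 36.0% | 68.0% |

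For b = 10%: 1 - 0.8 × 0.9 = 28%, and 1 - 0.4 × 0.9 = 64%.

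**Chance that a group is affected.** The SAP has no figure on this point to reproduce. Its Table 4 uses the same binomial formula, and all its entries recompute to rounding; for example, 1 - 0.9^10 = 65.1% for n=10 and a 10% rate. Read for b = 10%, that is the chance that a group of 10 contains at least one participant with a pre-dose symptom. The chance of at least one who is counted only for that reason is smaller, at 1 - (1 - b(1 - p))^n:

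- p = 20%: 1 - 0.92^10 = 56.6%, with an expected number of 10 × 0.08 = 0.8.
- p = 60%: 1 - 0.96^10 = 33.5%, with an expected number of 10 × 0.04 = 0.4.

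**The case against.** Counting every post-dose symptom is the cautious choice for a primary safety endpoint, and no formal hypothesis test depends on it (Section 6.8). The pre-dose grades are reported by symptom and severity in Tables 231-250 and by participant in Listing 9. Figures 579-653 also show symptoms by day for each participant. In arms this small a careful reader could trace carry-over. A rule requiring worsening could also drop a genuine new mild headache on Day 3 because an unrelated mild headache was noted before the injection. All of this stands. It is the reason to keep the existing count as the main one and not replace it.

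Several stronger readings are tempting, but the SAP does not support them:

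- **That the relatedness convention inflates the rates.** It enters no solicited rate.
- **That Section 4.5 contradicts itself by requiring worsening for some events and not for others.** The baseline rule concerns a medical condition present at screening, which the schedules place 1 to 30 days before Day 1. It does not mention the symptom check just before injection.
- **That the pre-dose data are ignored.** They are tabulated and listed, but not linked to the main counts.
- **That Figures 561-569 show such symptoms as new on Day 1.** The SAP does not define onset, so their treatment there is unknown.
- **That the Grade 3 alternate-etiology field in Listing 9 should remove events from the rates.** That would rest on attribution in an open-label study.

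**Conclusion.** The point holds as a limited gap in the main summaries. As specified, Tables 222-230 and the systemic row of Tables 212-216 count an unchanged pre-dose systemic symptom as a post-vaccination event, although the grade needed to separate the two is collected. A reader might infer that the reported rates do contain pre-existing complaints. The SAP supports only that they can, because it gives no pre-dose prevalence.

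The weight per participant (8.3 to 33.3 points) is arithmetic on the planned group sizes and applies only to someone who would not otherwise have reacted. For the Stage 2 dose groups, planned at 7 to 12, it is at most 14.3 points. The shifts from 20% to 28% and from 60% to 64% rest on an assumed 10% prevalence, persistence after dosing, and independence from new onset. The distortion shrinks as the true reaction rate rises. This is a worthwhile and cheap improvement in interpretability; it does not invalidate the safety analysis.

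**What to change.** Keep the all-post-dose count as the main summary. Add a second column to Tables 222-230, and to the systemic solicited row of Tables 212-216, that counts a systemic symptom only if its worst post-dose grade exceeds that participant's pre-dose grade for the same symptom and dose. For the row covering any systemic symptom, a participant qualifies if at least one systemic symptom does. For the any-dose tables, a participant qualifies if either dose does, each compared with its own pre-dose grade. Say in Section 9.3.1 how a missing pre-dose grade is handled. Local symptoms are unaffected because they have no pre-dose assessment.

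Leave the related-by-convention sentence in Section 4.5 and the Grade 3 alternate-etiology field as they are.

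The cost is a sentence or two of SAP text, one derived flag per symptom and dose, and one extra column; no new data are needed. The added column will miss a genuine new episode at the same grade as the pre-dose symptom, but the main column beside it still shows that event.

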#### Solicited Adverse Events

Solicited AEs are anticipated local and systemic AEs for which consistent collection of information is desired. Study clinicians will follow and collect resolution information for any reactogenicity symptoms that are not resolved within 7 days.

Solicited AEs will be collected using a memory aid and confirmed data recorded on the appropriate DCF from the time of each vaccination through 7 days post each vaccination.

For this study, solicited AEs will be:

- Injection site Pain
- Injection site Tenderness
- Injection site Erythema
- Injection site Edema/Induration
- Headache
- Fatigue
- Malaise
- Myalgia
- Arthralgia
- Nausea
- Fever
- Chills
- Diarrhea

### Unsolicited Adverse Events

All AEs spontaneously reported by the participant and/or in response to an open question from study staff or revealed by observation, physical examination or other diagnostic procedures must be recorded on the appropriate DCF.

Unsolicited AEs of all severities will be reported from the time of study product administration through 28 days post each vaccination.

After 28 days post last vaccination through the end of study, only SAEs, AESIs (including PIMMCs, NOCMCs, and MAAEs), and AEs leading to withdrawal from the study will be reported.

### Serious Adverse Events

An SAE is defined in 21 CFR 312.32 as follows: “An AE or suspected adverse reaction is considered serious if, in the view of either the participating site PI or appropriate sub-investigator or the sponsor, it results in any of the following outcomes:

- Death
- a life-threatening AE
- inpatient hospitalization or prolongation of existing hospitalization
- a persistent or significant incapacity or substantial disruption of the ability to conduct normal life functions
- or a congenital anomaly/birth defect

Important medical events that may not result in death, be life-threatening, or require hospitalization may be considered serious when, based upon appropriate medical judgment, they may jeopardize the patient or participant and may require medical or surgical intervention to prevent one of the outcomes listed in this definition. Examples of such medical events include allergic bronchospasm requiring intensive treatment in an emergency room or at home, blood dyscrasias or convulsions that do not result in inpatient hospitalization, or the development of drug dependency or drug abuse.”

“Life-threatening” refers to an AE that at occurrence represents an immediate risk of death to a participant. An event that may cause death if it occurs in a more severe form is not considered life-threatening. Similarly, a hospital admission for an elective procedure is not considered an SAE.

All SAEs, as with any AE, will be assessed for severity and relationship to study intervention.

All SAEs will be recorded on the appropriate SAE DCF.

All SAEs will be followed through resolution or stabilization by a study clinician, licensed to make medical diagnoses and listed on the Form FDA 1572 as the participating site PI or appropriate sub-investigator.

All SAEs will be reviewed and evaluated by DMID and will be sent to the DSMB (for periodic review unless related) and IRB/IEC as needed.

### Adverse Events of Special Interest (AESIs)

An adverse event of special interest (serious or nonserious) is one of scientific and medical concern specific to the sponsor’s product or program, for which ongoing monitoring and rapid communication by the investigator to the sponsor can be appropriate. Such an event might warrant further investigation in order to characterize and understand it. Depending on the nature of the event, rapid communication by the trial sponsor to other parties (e.g., regulators) might also be warranted. For this study, protocol specified AESIs are serologically or

virologically confirmed SARS-CoV-2 infection, severe COVID-19 to evaluate for potential episodes of vaccine-induced immune disease enhancement, myocarditis/pericarditis, Guillain-Barré Syndrome (GBS), and (Thrombosis with Thrombocytopenia Syndrome) TTS/Vaccine-Induced Immune Thrombotic Thrombocytopenia (VITT). Protocol-specified AESIs also include Medical Dictionary for Regulatory Activities (MedDRA®) Preferred Terms (PTs) and text strings as proposed by the Centers for Disease Control and Prevention (CDC) for surveillance of TTS events [1]. In addition, specified AESIs include any PTs included in the Standard MedDRA Query (SMQ) “embolic and thrombotic events”, including the PTs listed under the following SMQs, active as of 15JUL2021 in MedDRA dictionary 24.0: Embolic and thrombotic events, arterial; Embolic and thrombotic events, venous; and Embolic and thrombotic events, vessel type unspecified and mixed arterial and venous. These AESIs also include PTs incorporated into Section 4.6 of the CDC Vaccine Adverse Event Reporting System (VAERS) Standard Operating Procedures for COVID-19 [2], and the Brighton Collaboration AESIs relevant to vaccination that are listed below:

- New Onset Chronic Medical Conditions (NOCMCs) – defined as any new ICD diagnosis (per current International Statistical Classification of Diseases and Related Health Problems) that is applied to the participant during the course of the study, after receipt of the study agent, that is expected to continue for at least 3 months and requires continued health care intervention.
- Medically Attended Adverse Events (MAAEs) – defined as hospitalization, an emergency room visit or an otherwise unscheduled visit to or from medical personnel for any reason.
- Potentially Immune-Mediated Medical Conditions (PIMMCs) – These constitute a group of AEs that includes diseases which are clearly autoimmune in etiology and other inflammatory and/or neurologic disorders which may or may not have autoimmune etiology. PIMMCs that are of special interest for this study are Brighton Collaboration AESIs relevant to vaccination that include: seizures, GBS, acute disseminated encephalomyelitis, vasculitides, anaphylaxis, vaccine-associated enhanced respiratory disease, myocarditis/pericarditis, thrombocytopenia, and thrombotic events.

All AESIs are assessed, recorded, and followed as described above under AEs.

